#### Intensity of adverse event

The intensity of the AE should be judged based on the following:

Mild: Awareness of sign(s) or symptom(s) which is/are easily tolerated

Moderate: Enough discomfort to cause interference with usual activity

Severe: Incapacitating or causing inability to work or to perform usual activities

#### Pregnancy:

In rare cases, pregnancy might occur in a study. Once a subject has been enrolled into the study, after having taken Prizbind®, the investigator must report any drug exposure during pregnancy, which occurred in a female subject or in a partner to a male subject to the Sponsor by means of Part A of the Pregnancy Monitoring Form. The outcome of the pregnancy associated with the drug exposure during pregnancy must be followed up and reported by means of Part B of the Pregnancy Monitoring Form.

In the absence of a reportable AE, only the Pregnancy Monitoring Form must be completed

The investigator will report the Pregnancy Monitoring Forms as soon as possible via the unique entry point described in the Site Materials.

#### Information required

For each reportable adverse event, the investigator should provide the information requested on the appropriate CRF pages.

#### Reporting of related Adverse Events associated with any other BI drug

The investigator is encouraged to report all adverse events related to any BI drug other than the Prizbind® according to the local regulatory requirements for spontaneous AE reporting at the investigator's discretion by using the locally established routes and AE report forms. The term AE includes drug exposure during pregnancy, and, regardless of whether an AE

occurred or not, any abuse, off-label use, misuse, medication error, occupational exposure, lack of effect, and unexpected benefit.

AEs occurring from the patients whom used Prizbind after 15 April 2019 will not be collected in the CRF. These events will be reported spontaneously according to local regulations.

### **11.3 REPORTING TO HEALTH AUTHORITIES**

Adverse event reporting to regulatory agencies will be done by the MAH according to local and international regulatory requirements.

## **12. PLANS FOR DISSEMINATING AND COMMUNICATING STUDY RESULTS**

The interim and final results will be submitted to PMDA in Japanese Periodic Safety Update Report (PSUR) and re-examination documents. And the interim and final results including case reports are also planned to be used for related publications.

## **ANNEX 1. LIST OF STAND-ALONE DOCUMENTS**

Not applicable

2. LIST OF ABBREVIATIONS

Term	Definition / description
ADR	Adverse Drug Reaction
ADS	Analysis data set
AE	Adverse Event
aPTT	activated Partial Thromboplastin Time
BMI	Body Mass Index
CCr	Creatinine clearance
DBP	Diastolic Blood Pressure.
FFP	Fresh frozen plasma
GI	Gastrointestinal
ICH	Intracranial Hemorrhage
LLT	Lowest Level Term
MedDRA	Medical Dictionary For Regulatory Activities
NIS	Non-interventional Study
PCC	Prothrombin Complex Concentrate
PMS	Post Marketing Surveillance
PR	Pulse Rate
PT	Preferred Term
PV	Protocol Violation
Q1	Lower Quartile
Q3	Upper Quartile
RBC	Red Blood Cell
SAE	Serious Adverse Event
SBP	Systolic Blood Pressure
SD	Standard Deviation
SOC	System Organ Class
TIA	Transient Ischemic Attack
TSAP	Trial Statistical Analysis Plan
ULN	Upper Limit of Normal

3. INTRODUCTION

The purpose of this document is to provide a more technical and detailed elaboration of the principal features of the analysis described in the protocol, and to include detailed procedures for executing the statistical analysis of the primary and secondary variables and other data.

This TSAP assumes familiarity with the Non-interventional Study (NIS) protocol, including Protocol Amendments. In particular, the TSAP is based on the planned analysis specification as written in NIS protocol Section 9.7 “DATA ANALYSIS”. Therefore, TSAP readers may consult the NIS protocol for more background information on the study, e.g., on study objectives, study design and population, treatments, definition of measurements and variables, planning of sample size.

SAS® Version 9.4 will be used for all analyses.

4. CHANGES IN THE PLANNED ANALYSIS OF THE STUDY

There has been no change in the planned analysis from the statistical methods described in the NIS protocol.

5. ENDPOINT(S)

5.1 PRIMARY ENDPOINT(S)

There is no primary endpoint for effectiveness, the primary objective of the PMS study is the evaluation of safety (see the NIS protocol Section 9.3.2.1).

5.2 SECONDARY ENDPOINT(S)

[figure not shown]
5.2.1 Key secondary endpoint(s)

[figure not shown]
This section is not applicable as no key secondary endpoint has been specified in the protocol.

[figure not shown]
5.2.2 Secondary endpoint(s)

[figure not shown]
The secondary objective of the PMS study is following variable (refer to the NIS protocol Section 9.3.2.2).

- Reversal of anticoagulation as measured by coagulation tests (aPTT)
The maximum effect on the anticoagulant activity within 4 hours after the completion of administration:
Maximum Reversal: $\{ (\text{predose aPTT} - \text{minimum postdose aPTT}) / (\text{predose aPTT} - \text{ULN}) \} \times 100\%$
ULN: upper limit of normal in each site

6. GENERAL ANALYSIS DEFINITIONS

6.1 TREATMENT(S)

For basic study information on treatments, please refer to NIS protocol Section 9.1. The technical specification for treatment set-up is described in the analysis data set (ADS) plan. For effectiveness analyses, data up to 4 hours 30 minutes after last treatment intake will be considered as on treatment for aPTT. For safety analyses, data up to 5 days after last treatment intake will be considered as on treatment for AE.

6.2 IMPORTANT PROTOCOL VIOLATIONS

The following table defines the different categories of important PVs. The right-most column describes which PVs will be used to exclude patients from the different patient analysis sets. The final decision about which patients will be excluded from analysis sets will be taken during the course of the study and at report planning meetings before database lock at the latest.

Table 6.2: 1 Important protocol violations

Category / Code		Description	Requirements	Detection method	Excluded from
A		Entrance criteria not met			
	A1	Off-label use	Reason of use is “Other” only.	Automated	Effectiveness
	A2	No treatment with Prazaxa		Automated	Effectiveness
B		Trial medication			
	B1	No treatment with Prizbind		Automated	Safety
C		Missing data			
	C1	No all effectiveness data	There is none of following effectiveness data:a pair of predose/postdose aPTT, date/time of hemostasis, bleeding category and information about re-start anticoagulant therapy	Automated	Effectiveness
D		Trial specific			
	D1	Duplicated registration	In different patient number, sex, birthday, start date of first administration of Prizbind, height, weight and site name are the same.	Manual	Safety
	D2	Registration rule not followed	See the NIS protocol Section 9.2.2.2 and 9.2.2.3	Manual	Safety
	D3	Site contract is not valid		Manual	Safety

6.3 SUBJECT SETS ANALYSED

The safety set will be the basis of all demographic, baseline and safety analyses. Effectiveness analysis will be on basis of the effectiveness set.

- Safety set:

[figure not shown]
This patient set includes all patients who had no invalid registration, who were documented to have taken at least one dose of Prizbind.

[figure not shown]
- Effectiveness set:

[figure not shown]
This patient set includes all patients with Prizbind in the safety set who have at least one available effectiveness data.

[figure not shown]
Table 6.3: 1 Subject sets analyzed

Class of endpoint	Subject set								
	Safety set					Effectiveness set			
	All	Group A	Group B	Group A+B	Other	All	Group A	Group B	Group A+B
Primary endpoints	X								
Secondary endpoint					X				
Disposition	X								
Demographic and baseline characteristics									
Medical history/concomitant diseases									
Concomitant medication	X								
Concomitant therapies									
Baseline coagulation test									
Treatment exposure									
Termination of PMS									
Bleeding assessment	X				X				
Surgery / invasive procedure assessment		X			X				

6.5 POOLING OF CENTRES

This section is not applicable because centre/country is not included in the statistical model.

6.6 HANDLING OF MISSING DATA AND OUTLIERS

Missing or incomplete AE dates are imputed according to BI standards (see “Handling of missing and incomplete AE dates”) [\(1\)](#).

For missing of the end date of follow up period, the last date of all dates in CRF is imputed. If the end date of follow up period is entered, but earlier than the last date of all dates in CRF, the end date of follow up period is replaced by the last date of all dates in CRF.

6.7 BASELINE, TIME WINDOWS AND CALCULATED VISITS

With regard to effectiveness and safety endpoints, the term “baseline” or “predose” refers to the last observed measurement prior to administration of Prizbind.

In this analysis, 1st day is defined as first starting day of administration for Prizbind.

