## **9.2.3 Study visits**

Collected data should be reported as those to the closest available time (see [Table 1](#)).

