##### Demographics:

- Dabigatran Use(start date, daily dose, times/day, date and time of last intake)
- Prizbind® purpose of use(life-threatening or uncontrolled bleeding, emergency surgery/urgent procedures, other)
- Bleeding location, severity, start date and time, bleeding related to trauma
- Type of surgery/urgent procedure
- In/out patient
- Gender
- Age (birth year)
- Height
- Weight
- hypersensitive disposition
- Pregnancy
- Medical history/concomitant diseases
- History of bleeding events
- Department (emergency, cardiovascular, Neurosurgery, Neurology, Gastroenterolog, other)
- Participation of dabigatran clinical trial

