7.5.1 Key secondary endpoint(s)

This section is not applicable as no key secondary endpoint has been specified in the protocol.

7.5.2 (Other) Secondary endpoint(s)

The analysis for secondary endpoints will be performed for patients (aPTT at baseline >ULN) on the effectiveness set, as defined in the NIS protocol Section 9.3.2.2. N / Min / Q1 / Median / Q3 / Max will be displayed. If calculated reversal is > 100, it will be set to 100. The values will be capped at 100%.

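### The predose aPTT has no maximum age and no link to the last dabigatran intake, so a change in aPTT before dosing can enter maximum reversal, in either direction

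*SAP*

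**What the plan says.** The only named secondary outcome is maximum reversal of aPTT: (predose − minimum postdose) / (predose − ULN) × 100% (Protocol 9.3.2.2, SAP 5.2.2).

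- **Predose side.** SAP 6.7: baseline or predose "refers to the last observed measurement prior to administration of Prizbind". No maximum age is given, and dabigatran intake is not mentioned.
- **Postdose side.** This is bounded: "The maximum effect on the anticoagulant activity within 4 hours after the completion of administration" (SAP 5.2.2), and "data up to 4 hours 30 minutes after last treatment intake will be considered as on treatment for aPTT" (SAP 6.1).
- **Entry.** SAP 7.5.2 analyses "patients (aPTT at baseline >ULN) on the effectiveness set", so the same predose value decides who is counted. For the effectiveness set, SAP Table 6.2:1 lists "a pair of predose/postdose aPTT" among the qualifying data, without an age rule.
- **Cap.** "If calculated reversal is > 100, it will be set to 100" (SAP 7.5.2). No lower bound is stated.
- **Timing of data.** Protocol 9.2.3: "Collected data should be reported as those to the closest available time". Coagulation values are collected where applicable (9.3.3). Sites may be contracted after dosing (9.1), and their data are then limited to the medical chart (9.9).
- **Intake time.** The baseline items include "Dabigatran Use(start date, daily dose, times/day, date and time of last intake" (Protocol 9.3.3). The visible endpoint text does not use it.

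SAP 5.4 and 6.4 are not in the public text. Section 6.7 appears complete.

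**The concern.** Taking the last value before dosing is a usual baseline rule. It works well when the protocol schedules a sample just before treatment. Here no such sample is scheduled, so the age of the predose value is whatever routine care produced.

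The predose value does three jobs: it stands in the numerator, it stands in the denominator, and it decides entry to the analysis. If aPTT changed between the sample and the infusion, that change is attributed to Prizbind. A sample drawn before the last dabigatran dose does not measure the effect that Prizbind is given to reverse. The study is a single cohort, so no control group shows how much aPTT would have changed without the drug.

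**Working it through.** **The plan's own figures.** The plan states no expected value or precision for this endpoint, so there is nothing to reproduce. Its study-size claim does reproduce (at least one case of a 1% ADR among 300: 1 − 0.99^300 = 0.951) but has no bearing on aPTT.

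**Algebra from the SAP formula.** Let S be the aPTT in the sample used, T the true aPTT at dosing, and m the postdose minimum.

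- Reported: R_S = 1 − (m − ULN)/(S − ULN).
- True: R_T = 1 − (m − ULN)/(T − ULN).
- Both are capped at 100%.

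With S above ULN, so that the patient is analysed:

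1. T > ULN, m > ULN and S > T (aPTT fell before dosing): R_S > R_T, overstated.
2. T > ULN, m > ULN and S < T (aPTT rose before dosing): R_S < R_T, understated.
3. T > ULN and m ≤ ULN: both are 100% after the cap, so there is no bias.
4. T ≤ ULN and m ≤ ULN: the patient had no elevation left to reverse but scores 100%.

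**Size, first illustration.** Assumptions, not in the documents: the excess over ULN halves every h hours, there is no drug effect, and the postdose value is taken at 4 h. Apparent reversal is then 1 − 0.5^((age of sample + 4)/h).

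| h | Fresh sample | 12 h old sample | Added by age |
|---|---|---|---|
| 8 h | 29.3% | 75.0% | 45.7 points |
| 12 h | 20.6% | 60.3% | 39.7 points |
| 24 h | 10.9% | 37.0% | 26.1 points |

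Only the last column is due to the age of the sample. (Subtracting the rounded 21% from 60% gives 39.)

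**Size, second illustration.** Assumptions: ULN 40 s, aPTT without dabigatran 30 s, excess over 30 s halving every 6 to 18 h, and T = 60 s.

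- True reversal 0% (m = 60): a 4 h old sample reports 20 to 47%, a 12 h old one 47 to 82%. For example, at 4 h with a 12 h half-life, S = 30 + 30 × 2^(4/12) = 67.8, and (67.8 − 60)/(67.8 − 40) = 28%.
- True reversal 80% (m = 44): a 4 h old sample reports 84 to 89%, a 12 h old one 89 to 96%.

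**Entry.** Under the same assumptions but with T = 38 s, already below ULN, an 8 h old sample reads 40.9 to 50.2 s. The patient is analysed. With m at 38 s or lower the score is 100%.

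**Opposite direction.** With S = 45, T = 60 and m = 44, the report is (45 − 44)/(45 − 40) = 20% against a true (60 − 44)/(60 − 40) = 80%. With m = 48 the report is −60% against a true 60%.

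**The case against.** The case against runs as follows.

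- **The gap may be short.** Protocol 9.1 describes patients who need dabigatran's effect undone quickly. Every aPTT from the observation period is to be entered, and Protocol 9.2.3 points sites to the nearest value, so the last predose value is the freshest on record. This stands as a reason to expect modest gaps in many patients. It does not bound them, and the documents give no data.
- **The drug works and the cap absorbs much of the error.** Protocol 7 reports that idarucizumab neutralised dabigatran. For patients above ULN at dosing who reach ULN or below, the age of the sample does not matter. This stands. It leaves patients with partial reversal and those already normal at dosing.
- **The stakes are limited.** The endpoint is descriptive, untested and not part of the sample-size reasoning. The primary outcome is safety, and Protocol 9.9 already disclaims causal conclusions. This stands, and it limits the weight of the point.
- **A fixed window is arbitrary.** A 4 h limit, mirroring the postdose side, would still show 1 − 0.5^(8/12) = 37% (21 to 50%) with no drug effect in the first illustration. This stands against making 4 h the main analysis.
- **Times may be missing.** Protocol 9.3.3 lists no clock time for aPTT, and charts at sites contracted after dosing may be incomplete. The 4-hour endpoint nevertheless cannot be derived without timed samples.

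A reader might infer that natural dabigatran clearance is being counted as reversal throughout, so that the endpoint is inflated. The documents do not support that: the gap is unknown, many patients may be unaffected, and the error can run downward. Nor can the 60% at 12 h be read as the bias, because 20.6 points of it are decline after dosing that a fresh baseline would also show.

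**Conclusion.** The gap is real but limited. The SAP bounds the postdose aPTT and leaves the predose aPTT unbounded, in a study where sampling is unscheduled. Reported reversal can therefore be too high or too low when the postdose minimum stays above ULN, and a patient with nothing left to reverse can be counted as fully reversed.

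The size cannot be stated for this study, because neither the share of patients with old or pre-intake samples nor the intervals are given. The added 26 to 46 points apply to a 12 h old sample with no drug effect. With a true reversal of 80%, the second illustration puts the overstatement for a 4 h old sample at 4 to 9 points. Both illustrations rest on assumed half-lives, and the second also on assumed aPTT values.

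A reader might also infer that the error could never be separated afterwards. That goes too far: where sample, intake and dosing times exist, a restricted analysis can be done. The point is that the visible plan does not include one. The primary safety outcome is unaffected. This is a cheap improvement to a descriptive secondary endpoint, not a flaw in the study's main purpose.

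**What to change.** In SAP 6.7 and 7.5.2:

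1. Do not use as predose an aPTT known to have been drawn before the last recorded dabigatran intake. Report how many patients this removes. Keep patients whose intake time is unknown in the main analysis, and flag them.
2. Tabulate the interval from the predose sample to the start of Prizbind: N, median, quartiles and range.
3. Add a sensitivity analysis of maximum reversal limited to predose samples within a pre-specified short interval before the first infusion. The sponsor should choose the length and justify it.

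The cost is SAP wording, one derived interval and one repeated table, from data already collected or needed for the endpoint. The downsides are a smaller N in the restricted analysis and, for sites contracted after dosing, some missing sample or intake times, which should be counted and reported. If few samples are old, the interval table will show that the result is robust.

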7. PLANNED ANALYSIS

For End-Of-Text (EoT) tables, the set of summary statistics is: N / Mean / SD / Min / Q1 / Median / Q3 / Max.

For tables that are provided for endpoints with some extreme data, median, quartiles and percentiles should be preferred to mean, standard deviation, minimum and maximum.

Tabulations of frequencies for categorical data will include all possible categories and will display the number of observations in a category as well as the percentage (%) relative to the respective treatment group (unless otherwise specified, all patients in the respective patient set whether they have non-missing values or not). Percentages will be rounded to two decimal places. The category missing will be displayed only if there are actually missing values.

Tables will be displayed by purpose of use (Group A, Group B, Group A+B, Other and All) categorized by trial team.

In addition, individual values on demographics, safety and effectiveness will be presented in subject data listings.

7.1 DEMOGRAPHIC AND OTHER BASELINE CHARACTERISTICS

Only descriptive statistics are planned for this section of the report.

7.2 CONCOMITANT DISEASES AND MEDICATION

Concomitant diseases will be coded by the latest version of Medical Dictionary for Regulatory Activities (MedDRA). Frequency of patients with concomitant diseases will be summarized by system organ class (SOC) and preferred term (PT).

Concomitant diseases: Diseases that are suffering from at the first administration of Prizbind.
Concomitant medication will be coded by latest version of 'Nihon-iyakuhinshu'.

7.3 TREATMENT COMPLIANCE

Compliance data is not collected in this study.

7.4 PRIMARY ENDPOINT(S)

The analysis of the primary endpoint is described in [Section 7.8.1](#).

7.5 SECONDARY ENDPOINT(S)

[figure not shown]
7.5.1 Key secondary endpoint(s)

This section is not applicable as no key secondary endpoint has been specified in the protocol.

7.5.2 (Other) Secondary endpoint(s)

The analysis for secondary endpoints will be performed for patients (aPTT at baseline >ULN) on the effectiveness set, as defined in the NIS protocol Section 9.3.2.2. N / Min / Q1 / Median / Q3 / Max will be displayed. If calculated reversal is > 100, it will be set to 100. The values will be capped at 100%.

7.7 EXTENT OF EXPOSURE

Only descriptive statistics are planned for this section of the report.

7.8 SAFETY ANALYSIS

All safety analyses will be performed on the safety set.

7.8.1 Adverse events

Unless otherwise specified, the analyses of adverse events (AEs) will be descriptive in nature. All analyses of AEs will be based on the number of patients with AEs. In the tabulation of ADRs, serious ADRs, important identified risks and important potential risks by SOC and PT, not only the number of patients but also number of events will be displayed. AEs with onset date prior to treatment of Prizbind which lead to death after Prizbind administration are not included in AE analysis but will be used when calculating time to death using Kaplan Meier survival estimates.

For analysis multiple AE occurrence data on the CRF will be collapsed into an AE provided that all of the following applies:

- All AE attributes are identical (LLT, intensity, action taken, therapy required, seriousness, reason for seriousness, relationship, outcome).
- The occurrences were time-overlapping or time-adjacent (time-adjacency of 2 occurrences is given if the second occurrence started on the same day or on the day after the end of the first occurrence).

For further details on summarization of AE data, please refer to (2).

All adverse events occurring after the residual effect period will be assigned to 'post-treatment. The frequency and percentages of ADRs, AEs, serious adverse events (SAEs), important identified risks and important potential risks occurred in treatment + post-treatment period as well as treatment period will be tabulated. For details on the treatment definition, see [Section 6.1](#). Also, ADRs and SAEs up to 28 days after last treatment intake (=observation period) will be tabulated.

An overall summary of AEs will be presented.

The frequency of patients with ADRs will be tabulated by Prizbind dose at onset, SOC and PT according to the most recent MedDRA version.

Separate tables will be provided for patients with SAEs, serious ADRs and for patients with each of the following AEs for important identified risks: hypersensitivity (shock and anaphylaxis) and important potential risks: immunogenicity, thrombotic event (ischemic stroke, myocardial infarction, pulmonary embolism, deep vein thrombosis, systemic embolism). Important identified risks and important potential risks are defined in accordance with the Japanese RMP. The details of these risks are defined in the external file

‘MedDRA_verxxx.xlsx (current ver.)’. The file is stored in BIRDS ‘Section 8 TSAP and programming’.

For AEs leading to discontinuation of Prizbind, a summary table will also be created based on patients who discontinued the treatment due to AEs.

In addition, summaries for the time to onset of first episode for the ADRs will be tabulated by duration, by primary SOC, and PT.

An ADR is defined as an AE for which either the investigator or the sponsor (or both) assess the causal relationship to Prizbind as “Yes”. The SOCs will be sorted according to the standard sort order specified by European medicines agency, PTs will be sorted by frequency (within SOC).

A serious AE is defined as an AE for which either the investigator or the sponsor (or both) assess the seriousness as “Serious”.

Mortality rate at the end of follow-up period will be calculated descriptively by KM estimate. It will be also stratified by ICH, upper or lower GI bleeds on-going at baseline assessment and other for Group A and Group A+B categorized by trial team.

To compare risks of overall ADR, SAE, serious ADR as well as each of the important potential risks in different patient subgroups, frequency tabulation stratified by different patient subgroups will be provided with odds ratios and exact 95% confidence intervals whenever specified (see [Section 6.4](#)).

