### 9.7.1 Main analysis

All outcome events are based on reported AE data which will be handled according to BI standards (see the section below).

[figure not shown]
The safety analysis will include all patients who registered, received the Prizbind® for Intravenous Solution 2.5 g treatment and collected CRF except for who meet the ineligible criteria (see Section 9.7).

[figure not shown]
AEs will be coded using the current version of the Medical Dictionary for Regulatory Activities (MedDRA). Based on the concept of treatment emergent AEs, all AEs occurring between first intake of Prizbind® for Intravenous Solution 2.5 g prescribed at baseline visit up to 5 days after the last intake will be considered 'treatment period'. In addition, AEs with onset date before start of the trial treatment but with worsening in intensity during the treatment will also be assigned to the on-treatment period. Other AEs will be assigned to the screening or post-treatment period, respectively.

An AE is considered to be an ADR if either the physician who has reported the AE or the sponsor assesses its causal relationship as 'related'.

The frequency and percentages of ADRs, SAEs, and other AEs occurred in treatment period as well as treatment + post-treatment period will be tabulated by system organ class and preferred term for all patients and for subgroups based on the important baseline characteristics (details will be described in the TSAP).

No imputation is planned for missing AE data except for missing onset dates which will be handled according to BI standard.

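### SAP 7.8.1 excludes every fatal AE with pre-dose onset from the AE analysis, whereas protocol 9.7.1 tabulates pre-dose AEs that worsen during treatment and makes no exception for death

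*SAP*

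**What the plan says.** Protocol 9.7.1 sorts AEs into periods. The treatment period runs from first intake to 5 days after last intake. For events that began earlier it names the on-treatment period as the destination if they worsened: "AEs with onset date before start of the trial treatment but with worsening in intensity during the treatment will also be assigned". For the remainder, "Other AEs will be assigned to the screening or post-treatment period, respectively". It then sets the tables, broken down by system organ class and preferred term: "The frequency and percentages of ADRs, SAEs, and other AEs occurred in treatment period as well as treatment + post-treatment period will be tabulated". None of these sentences makes an exception for fatal events.

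SAP 7.8.1 has a separate rule for fatal events: "AEs with onset date prior to treatment of Prizbind which lead to death after Prizbind administration are not included in AE analysis". The same sentence says that these events "will be used when calculating time to death using Kaplan Meier survival estimates", and later in the section: "Mortality rate at the end of follow-up period will be calculated descriptively by KM estimate". There is no exception for events that worsened after dosing.

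SAP 6.1, to which 7.8.1 refers for the treatment definition, gives only the 5-day limit for AEs and is silent on worsening. SAP section 4 states: "There has been no change in the planned analysis from the statistical methods described in the NIS protocol".

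**The concern.** A fatal AE that began before dosing and worsened during treatment is in the tables under the protocol and out of them under the SAP. A programmer who follows the SAP as written would drop it, and nothing in SAP section 4 would tell a reader that this departs from the protocol.

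The event would be dropped because it was fatal. An event with the same course that the patient survived, if reported, is not touched by the SAP sentence. Serious AEs are among the safety outcomes in protocol 9.3.2.1, and death makes an AE serious under protocol 11.1, so every event in this class is an SAE. Fatal AEs are also one of only two AE categories that protocol 11.2 requires on the CRF; the other is ADRs. The SAE tables by subgroup, with their odds ratios (SAP 7.8.1), would carry the same omission.

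**Working it through.** The plan gives no figure to reproduce here. The check sets the two rules against each type of fatal AE that began before dosing.

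| Course of the event | Protocol 9.7.1 | SAP 7.8.1 | Do they agree? |
|---|---|---|---|
| Does not rise in intensity | Screening period, not tabulated | Left out | Yes |
| Rises during the infusion or bolus; pre-dose onset date kept | On-treatment, tabulated | Left out | No |
| Rises later, up to 5 days after last intake; pre-dose onset date kept | Depends on what the worsening clause means by treatment | Left out | No, if the clause means the 5-day period; otherwise yes |
| Rises after that; pre-dose onset date kept | Screening period, not tabulated | Left out | Yes |
| Rise recorded as a separate occurrence with its own post-dose onset | Tabulated | Tabulated, since the onset is not before dosing | Yes |

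Four conditions set the width of the conflict.

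1. **Window.** The worsening clause refers to the treatment and gives no number of days. Protocol 9.3.1 describes a bolus or two consecutive infusions of 5 to 10 minutes each, so the literal reading is a bolus or about 2 × 5 = 10 to 2 × 10 = 20 minutes of infusion. The wider reading runs to 5 days after last intake. The clause assigns such events to the on-treatment period, which makes the wider reading plausible, but the text does not settle it.
2. **Room to worsen.** Protocol 11.2 has three intensity grades, with severe at the top. An AE already severe before dosing cannot rise in grade.
3. **Recording.** The SAP collapsing rule merges occurrences only if all attributes match, intensity included. A worsened episode entered as its own occurrence therefore stays separate. The protocol clause, however, describes a worsened AE by its pre-dose onset date, and that is the record which the SAP sentence removes. The visible text does not say which form the CRF uses.
4. **Outcome.** The event must lead to death.

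For scale, let *k* be the number of patients in the conflict set who have no other event in the table concerned. The percentage under the SAP rule is then lower by *k*/300, with 300 the planned size from protocol 9.5. The documents give no value for *k*, so the values below are assumptions:

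- *k* = 0: no difference
- *k* = 1: 1/300 = 0.33 points
- *k* = 3: 3/300 = 1.00 point
- *k* = 9: 9/300 = 3.00 points

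SAP section 7 reports percentages to two decimals, so even one patient would change a reported figure.

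**The case against.** The best defence reads the two documents together. SAP section 3 says that the plan rests on protocol 9.7, and section 4 says that nothing changed. On that view the worsening rule still holds, and the SAP sentence removes only events that the protocol already places in screening. This may be what the authors meant. It needs an exception that the SAP sentence does not contain, however, and SAP 6.1 does not supply one.

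The second defence is that the class may be empty. One main reason for use is life-threatening or uncontrolled bleeding, and such an event would often already be at the top grade. Worsening may also be recorded as a new occurrence, a matter that could be settled in the SAP's reference on AE summarization, the sponsor's AE standards or the analysis data set plan, none of which is available here. This stands and limits the weight of the point.

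Third, the comparison with surviving patients is weaker than it looks. Non-fatal events judged unrelated need not be on the CRF at all, so the matching non-fatal case may often be missing from the data. This also stands.

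Finally, keeping progression of the presenting illness out of AE tables while counting every death in the survival estimate is a defensible choice. If it was made, section 4 is the place to declare it.

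**Conclusion.** The conflict is real, narrow and minor. As written, the SAP removes fatal AEs that the protocol tabulates, and section 4 says that nothing has changed. It reaches only fatal AEs that keep a pre-dose onset date and rise in intensity during the treatment, with that window undefined. The number affected cannot be derived and may be zero; each affected patient with no other event in the table is worth 0.33 points at 300 patients.

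A reader might infer more than the documents support:

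- **That deaths are lost.** They are not. They remain in the Kaplan-Meier estimate, and SAP section 7 plans subject listings of safety data.
- **That the whole exclusion contradicts the protocol.** It does not. For pre-dose AEs that do not worsen, both documents keep them out of the tables.
- **That any worsening up to 5 days after dosing is covered.** The protocol's worsening clause does not say so.
- **That the primary outcome is materially distorted.** An affected event enters the ADR tables only if the investigator or the sponsor judges it related, and protocol 11.2 lists pre-treatment onset as an argument against that. Any ADR effect is probably small.

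The conclusion assumes that the SAP sentence is applied as written and that at least some worsened AEs keep their original onset date.

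**What to change.** Limit the SAP 7.8.1 exclusion to fatal pre-dose AEs that do not meet the protocol's worsening rule. For example: *Pre-dose-onset AEs with death after Prizbind are left out of the AE analysis unless they meet the worsening rule of NIS protocol Section 9.7.1.* Keep the protocol's own phrase for worsening, and state in SAP 6.1 or 7.8.1 whether it means the administration itself or the period to 5 days after last intake. State also whether a worsened AE keeps its onset date or becomes a new occurrence. Flag the events that are kept in as *onset before dosing, worsened after dosing*.

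If the sponsor prefers the full exclusion, declare and justify it in SAP section 4 and list the affected patients.

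The cost is a few lines of SAP text and one flag; fatal AEs are already on the CRF. For bleeds, a worsened status with date and time is collected (protocol 9.3.3), but that is not the AE intensity grade, and the documents do not show whether the AE page dates a change in intensity. A few paper CRFs may need manual review, and because there is no monitoring and no direct access to source data (protocol 9.6 and 9.10.2.2), worsening may not always be establishable. The SAE frequency may also come to include some progression of the presenting event, which the flag makes visible.
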